9.4.3 ANALYSIS OF THE SECONDARY ENDPOINT(S)

For each biomarker and each scanner, $RC_{same-day,same operator}$ will be estimated as follows:

$$\widehat{RC}_{same-day,same operator} = 2.77 \times \sqrt{\sum_{i=1}^N (Y_{1i} - Y_{2i})^2 / 2\bar{Y}_i^2 N_j}$$

where Y_{1i} is the biomarker measurement at timepoint 1 and Y_{2i} is the replicate biomarker measurement on the same scanner by the same operator at timepoint 1 for the i^{th} participant. \bar{Y}_i is the mean of Y_1 and Y_2 for participant i . N_j is the total number of participants per scanner.

For each biomarker and each scanner, $RC_{diff-day,diff-operator}$ will be estimated as follows:

$$\widehat{RC}_{diff-day,diff-operator} = 2.77 \times \sqrt{\sum_{i=1}^N (Y_{1i} - Y_{2i})^2 / 2\bar{Y}_i^2 N_j}$$

where Y_{1i} is the biomarker measurement at timepoint 1 and Y_{2i} is the biomarker measurement on the same scanner by the same operator at timepoint 2 for the i^{th} participant. \bar{Y}_i is the mean of Y_1 and Y_2 for participant i . N_j is the total number of participants per scanner.

For each biomarker and a pair of scanners, $RDC_{scanner}$ will be estimated as follows:

$$\widehat{RDC}_{scanner} = 2.77 \times \sqrt{\sum_{i=1}^{N_{j,j'}} (Y_{1i} - Y_{2i})^2 / 2\bar{Y}_i^2 N_{j,j'}}$$

where Y_{1i} is the biomarker measurement at timepoint 1 and Y_{2i} is the biomarker measurement on a different scanner for the i^{th} participant. This RDC will be estimated both with the same and different operators, and on the same and different days. \bar{Y}_i is the mean of Y_1 and Y_2 for participant i . $N_{j,j'}$ is the number of participants scanned on the scanners j and j' .

For each biomarker and each scanner, 95% upper bounds for $RC_{\text{same-day,same-operator}}$, $RC_{\text{diff-day,diff-operator}}$, and RDC_{scanner} will be constructed as follows:

$$\widehat{RC} \sqrt{\frac{N}{\chi_{N,\alpha}^2}}$$

where $\chi_{N,\alpha}^2$ is the α th percentile of the chi square distribution with N degrees of freedom and α is 0.95.

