Secondary endpoints:

- Evaluation of pooled same-day, same-operator repeatability coefficient of ultrasound-based measurements of SWS.
- Evaluation of pooled different-scanner, same-day reproducibility coefficient of ultrasound-based measurements of SWS.
- Evaluation of same-day, same-operator repeatability coefficient of VCTE on the measurement of SWS and Young's modulus.
- Evaluation of different-day, different-operator reproducibility coefficient of VCTE on the measurement of Young's modulus.

Exploratory endpoints

- Precision and other reliability metrics of vendor- or device-specific investigational measurements of other components of NAFLD such as steatosis and possibly inflammation.

Study Population

This study will enroll patients with suspected or confirmed diagnosis of NAFLD. Based on protocol-specified FIB-4 values, about one-third are expected to have low, one-third to have intermediate, and one-third to have high likelihood of advanced fibrosis. The sample size of 40 participants was determined to provide sufficient sample to provide >80% power to qualify SWS (or equivalent) as an ultrasound (US)-based biomarker for advancement to Stage 2. The threshold for automatic qualification for advancement to Stage 2 will be an upper bound of the 95% confidence interval (CI) of the reproducibility coefficient less than 35%. Dropouts and technical failures were included in this sample size determination.

Sex: ~ 50:50 – Note- no stratification will be done based on sex

Age: ≥ 18 yrs

Demographic group: Patients with a high probability of NAFLD based on the eligibility criteria

General health status: Patients with suspected or confirmed diagnosis of NAFLD

Geographic location: San Diego, CA and Boston, MA (greater metropolitan areas)

Phase

N/A

[figure not shown]
Description of Sites/Facilities Enrolling Participants Planned facilities/participating sites enrolling participants: University of California- San Diego (UCSD) and Massachusetts General Hospital (MGH)
 Number of sites: 2

Description of Study Intervention Study will not have any therapeutic intervention. The goal of the study will be evaluating the variability of ultrasound-based measures for the diagnosis and monitoring of NAFLD/NASH.

Study Duration 12 months

Participant Duration < 1 month

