Participants will be consecutively assigned to their corresponding category until the category is closed (reaches maximum of 11). Once a category is closed at a given site, participants will no longer be enrolled into that category at that site.

Each participant will undergo ultrasound imaging at Visit 1 (by operator 1) and at Visit 2 (by operator 2), separated by 1 to 7 days. The 7-day window for Visit 2 is selected to allow flexibility in scheduling while helping to ensure that there is no substantial biological change in the interim. Ultrasound exams at Visits 1 and 2 will be performed at about the same time of day (target is ± 2 hours) and with identical fasting and other preparation instructions. For each visit, each participant will be assigned to three of the five ultrasound scanners plus VCTE. As shown in the Schema (**Section 1.2**), for Visit 1, two of the three ultrasound exams will be repeated; the third ultrasound exam and the VCTE exam will be performed once. For Visit 2, the third ultrasound exam and the VCTE exam will be repeated; the other two ultrasound exams will be performed once. The selection of exams to be repeated will be based on a block assignment strategy to ensure an approximately equal number of scans are performed by each ultrasound system, in addition to VCTE. Thus, each subject will undergo a total of six exams at each of their two visits, for a total of 12 exams across both visits. For the repeated exams, subjects will get off the table with a short break (target about 5 minutes) before getting back on the table. Subjects will not be required to leave the room. The machine will not be turned off and powered up again to save time

Ultrasound operators will follow the acquisition procedures outlined in the imaging manual. The imaging manual will address patient positioning, image acquisition and quality control with scanning protocol input from the relevant ultrasound vendors. Additional investigational ultrasound data may be acquired, including with use of non-FDA-approved vendor proprietary software.

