9.2 SAMPLE SIZE DETERMINATION

The following assumptions were made in determining sample size for the primary study objective:

1. Repeat measurements on the same participant follow a normal distribution.
2. $RDC_{\text{diff-day, diff-operator}}$ is in the range of 20-30% (wCV of 7.2-10.8%).
3. A balanced design is planned (i.e. equal number of participants per scanner) where the following scenarios describe the possible RDCs across the five scanners:
 - 25, 25, 25, 25, 25%
 - 24, 25, 25, 26, 27%
 - 23, 25, 25, 27, 29%
 - 23, 25, 25, 27, 30%
4. A study with 80% power is desired.

The null hypothesis for the primary study objective is $H_0: RDC_{\text{diff-day, diff-operator}} \geq 35\%$, versus the alternative hypothesis that $RDC_{\text{diff-day, diff-operator}} < 35\%$, where RDC is the reproducibility coefficient for different day and different operator. The upper 95% confidence bound for the RDC will be constructed.

A Monte Carlo simulation study was conducted to determine the sample size needed. For each simulated participant, two observations were generated from a normal distribution with the specified variance. Samples of varying size were simulated. From each sample $RDC_{diff-day, diff-operator}$ was estimated, along with its 95% CI. This process was repeated 10,000 times.

In the table below the sample size is reported such that 80% of the samples of that size met the precision qualification (i.e. upper 95% confidence bound for $RDC < 35\%$). The results suggest that by pooling across the five scanners, up to 55 independent observations are needed. With each subject scanned on three different scanners at the two time points and assuming moderate correlation between observations from the same subject ($r=0.25$), we consider the design effect to account for the clustering of the data (i.e. 3 observations/subject). The design effect is $1+(s-1)r$, where r =correlation and s =# of observation/subject, i.e. $1+(3-1)0.25=1.5$. Thus, $(55 \times 1.5)/3=27.5$ so a study with 28 total participants would provide 80% power.

For estimating the $RDC_{diff-day, diff-operator}$ of VCTE, assuming an $RDC_{diff-day, diff-operator}$ of 25%, 32 subjects provides 80% power to show that the $RDC < 35\%$. Taking into consideration the possibility of a drop-out or technical failure rate of no more than 25%, a study with 40 total participants (20 per site) is proposed.

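### The same-day repeatability formula in Section 9.4.3 takes both replicates at timepoint 1, but VCTE and one of each participant's three scanners are repeated only at Visit 2

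*Combined protocol and SAP*

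**What the plan says.** The secondary endpoints in Section 1.1 include both "Evaluation of pooled same-day, same-operator repeatability coefficient of ultrasound-based measurements of SWS" and "Evaluation of same-day, same-operator repeatability coefficient of VCTE on the measurement of SWS" (the latter also for Young's modulus).

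Section 9.4.3 gives one formula for same-day repeatability, for each biomarker and each scanner. Its first measurement is at timepoint 1 and its second is a "replicate biomarker measurement on the same scanner by the same operator at timepoint 1". The divisor is N_j, all participants on scanner j.

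Section 4.1 sets the exam pattern: "each participant will be assigned to three of the five ultrasound scanners plus VCTE". At Visit 1 two of the three ultrasound exams are repeated, and "the third ultrasound exam and the VCTE exam will be performed once". Then: "For Visit 2, the third ultrasound exam and the VCTE exam will be repeated; the other two ultrasound exams will be performed once". Operator 1 scans at Visit 1 and operator 2 at Visit 2.

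Timepoint is not formally defined. Section 9.2 describes the design as "With each subject scanned on three different scanners at the two time points", and Section 9.4.2 pairs timepoint 1 with timepoint 2 for the different-day, different-operator coefficient.

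**The concern.** If timepoint 1 is Visit 1, the formula asks for a VCTE replicate that is never taken there, and for a replicate on the third scanner that is not taken there either. The VCTE endpoint would have no data, and one third of the ultrasound replicates would be dropped. The VCTE gap would show at once. The ultrasound loss is easier to miss, because each scanner would still return an estimate, only a less precise one.

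The text around the formula does not resolve this. Where Section 9.4.3 wants more than one day used, for the between-scanner coefficient, it says so; the same-day definition has no such sentence. Nor does the section print a pooled same-day form or name VCTE. Without a correction, the choice of visits and divisor is left to the analyst.

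**Working it through.** **Check of the exam pattern (Section 4.1).** Visit 1: 2 scanners × 2 + 1 scanner × 1 + VCTE × 1 = 6. Visit 2: 2 × 1 + 1 × 2 + VCTE × 2 = 6. The total of 12 agrees with the protocol's own count.

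**Replicate pairs.** The inputs are 40 participants (Section 9.2) and the pattern above. The second row applies Section 9.2's ceiling of 25% for drop-out or technical failure: 40 × 0.75 = 30.

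| Completers | Ultrasound pairs at Visit 1 | Ultrasound pairs at Visit 2 | VCTE pairs at Visit 1 | VCTE pairs at Visit 2 |
|---|---|---|---|---|
| 40 | 2 × 40 = 80 | 1 × 40 = 40 | 0 | 40 |
| 30 | 2 × 30 = 60 | 1 × 30 = 30 | 0 | 30 |

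With 40 completers, 160 pairs are collected and the timepoint 1 rule admits 80: 80 of 120 for ultrasound and 0 of 40 for VCTE. With 30 it admits 60 of 120: 60 of 90 and 0 of 30. The proportions do not depend on the number of completers.

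**Per scanner, if Visit 1 repeats are balanced over the five systems.** 120/5 = 24 pairs, of which 80/5 = 16 are at Visit 1 and 40/5 = 8 at Visit 2. With 30 completers: 18, of which 12 and 6.

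**Precision.** With n pairs, the squared coefficient behaves approximately as a scaled chi-square on n degrees of freedom, so the relative standard error of the RC is about 1/√(2n).

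- Per scanner, 40 completers: 1/√32 = 17.7% with 16 pairs; 1/√48 = 14.4% with 24.
- Per scanner, 30 completers: 1/√24 = 20.4% with 12 pairs; 1/√36 = 16.7% with 18.
- VCTE: no estimate as written; 1/√80 = 11.2% with its 40 Visit 2 pairs; 1/√60 = 12.9% with 30.
- Pooled ultrasound, assuming that Section 9.2's design effect 1 + (s − 1) × 0.25 also holds for same-day pairs. Visit 1 pairs only (s = 2): 80/1.25 = 64 effective pairs, 1/√128 = 8.8%. All pairs (s = 3): 120/1.5 = 80 effective pairs, 1/√160 = 7.9%.

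**Which reading the divisor fits.** N_j is 40 × 3/5 = 24 under balance. Taking each scanner's pair from the visit where it was repeated gives 16 + 8 = 24 pairs, exactly N_j. Taking Visit 1 only gives 16.

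**The bound in Section 9.4.3.** It multiplies the estimate by √(N/χ²), with the percentile printed as 0.95. At 24 degrees of freedom that multiplier is 0.81, so the result lies below the estimate. The lower 5th percentile gives 1.32.

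**The case against.** The best defence is that timepoint 1 is loose wording for a single session, carried over from the two-visit formula. Three things support it. The subscript already states the condition: same day, same operator. The design repeats each device at exactly one visit, under one operator, so every participant supplies one valid pair per device, and Visit 2 replicates meet the condition as well as Visit 1 replicates do. And the printed divisor equals the pair count only if all those pairs are used. This stands as evidence of intent. It does not remove the conflict, because Sections 9.2 and 9.4.2 use timepoints for the two visits, and so does the next definition in Section 9.4.3.

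A reader might infer from the mismatch between 16 pairs and N_j = 24 that the RC will come out about 18% too low (√(16/24) = 0.816). That needs an analyst to sum 16 pairs and divide by 24. The documents do not direct this, and the divisor is better read as pointing to the inclusive definition than as a second defect. With a divisor that matches the pairs used, the loss is one of precision.

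It is also fair to say that the pooled loss is small (8.8% against 7.9%), that a pooled same-day form follows readily from the double sum in Section 9.4.2, and that correcting the sentence for VCTE would probably expose the ultrasound problem too.

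**Conclusion.** The inconsistency is real and should be corrected. Read literally, Section 9.4.3 leaves VCTE same-day repeatability with no estimate and uses two thirds of the ultrasound replicates. These totals rest only on timepoint 1 meaning Visit 1 and on complete, evaluable exams.

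The split of 16 of 24 is less firm. Section 4.1 promises roughly equal scan numbers per system, and each assigned scanner gets three scans per participant whichever visit holds the repeat. Equal scan totals therefore do not fix how the repeats divide between visits. The pooled standard errors borrow a correlation that Section 9.2 states for the different-day data.

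Two stronger conclusions are not supported. One is that the VCTE endpoint is lost: Section 4.1 schedules a Visit 2 replicate for every participant, so wording alone recovers it. The other is that the Stage 2 decision is at risk: the primary coefficient, the 35% criterion and the sample size do not use this formula.

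**What to change.** In Section 9.4.3:

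- Define Y1 and Y2 as the two same-day, same-operator replicates at whichever visit that exam was repeated: Visit 1 for two scanners, Visit 2 for the third scanner and VCTE.
- Set the divisor and the degrees of freedom to the number of participants with such a pair.
- State that the definition applies to VCTE and, summed over the five scanners with the total number of pairs as divisor, to the pooled ultrasound RC.
- As a minor correction, the different-day, different-operator definition should refer to a different operator at timepoint 2. It now refers to the same operator, against its own subscript and Sections 4.1 and 9.4.2. No pairs change.
- If the bounds are edited, for example by writing N_j for N, correct the chi-square percentile to the lower 5th at the same time. Changing N alone does not give an upper bound.

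The cost is a wording change to one section. It needs no new scans or data and no change to the design, the primary estimator or the sample size.

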9.4.2 ANALYSIS OF THE PRIMARY EFFICACY ENDPOINT(S)

$RDC_{diff-day, diff-operator}$ will be estimated as follows:

$$\widehat{RDC}_{diff-day,diff-operator} = 2.77 \times \sqrt{\sum_{j=1}^5 \sum_{i=1}^{N_j} (Y_{1ij} - Y_{2ij})^2 / 2\bar{Y}_{ij}^2 N}$$

where Y_{1ij} is the biomarker measurement at timepoint 1 and Y_{2ij} is the biomarker measurement on the same scanner j by a different operator at timepoint 2 for the i^{th} participant. \bar{Y}_{ij} is the mean of Y_1 and Y_2 for participant i for scanner j . N_j is the total number of participants per scanner, and N is the total number of observations. The 95% upper bound for $RDC_{diff-day,diff-operator}$ will be constructed as follows:

$$\widehat{RDC} \sqrt{\frac{N}{\chi_{N,\alpha}^2}}$$

where $\chi_{N,\alpha}^2$ is the α th percentile of the chi square distribution with N degrees of freedom and α is 0.95. A bootstrap 95% CI will also be constructed for RDC , where sampling with replacement will be performed at the subject level. If the upper 95% confidence bound is < 0.35 ($< 35\%$), then it will be concluded that the biomarker meets the prespecified precision criterion.

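### The same-day formula in 9.4.3 takes its replicates at timepoint 1, but VCTE and the third ultrasound scanner are repeated only at Visit 2; the declared pooled secondary coefficients also have no estimator

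*Combined protocol and SAP*

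**What the plan says.** The synopsis (section 1.1) includes, among its secondary endpoints, a pooled repeatability coefficient for ultrasound shear wave speed when one operator scans twice within a day. It also includes a pooled coefficient across scanners: "Evaluation of pooled different-scanner, same-day reproducibility coefficient of ultrasound-based measurements of SWS". A third is the matching within-day repeatability of VCTE, for shear wave speed and for Young's modulus; this one is not pooled.

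Section 9.4.3 gives the same-day, same-operator coefficient separately for each biomarker and scanner. Its second reading "is the replicate biomarker measurement on the same scanner by the same operator at timepoint 1", and its divisor N_j is defined as all participants on that scanner. The different-scanner coefficient is given "For each biomarker and a pair of scanners", with the number of participants scanned on both as its divisor. No formula in 9.4.3 sums over scanners or scanner pairs. Every bound there is a chi-square bound with N degrees of freedom.

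Section 4.1 assigns each participant three of the five ultrasound scanners plus VCTE. At Visit 1, two ultrasound exams are repeated, and the third ultrasound exam and VCTE are done once. "For Visit 2, the third ultrasound exam and the VCTE exam will be repeated". The remaining two scanners get a single exam at that visit.

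The only pooled formula is in 9.4.2, for the primary coefficient (same scanner, two timepoints, different operators). That section adds, for the primary coefficient: "A bootstrap 95% CI will also be constructed for" it, resampling participants.

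**The concern.** Section 9.4.2 reserves timepoint 2 for the different-day, different-operator reading, so timepoint 1 is Visit 1. With that meaning, the same-day formula looks for VCTE replicates at a visit where none are scheduled, and it misses the Visit 2 repeats of the third scanner. The divisor then counts participants who contribute nothing to the sum.

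The second gap is that two declared endpoints are pooled and have no pooled estimator. The analyst would have to decide, possibly after seeing data, which pairs, visits and readings to use and how many degrees of freedom to claim. For the different-scanner coefficient that choice matters, because three pairwise differences among three readings are not independent.

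At stake are the secondary precision figures, which section 3 says will refine the context of use for later trials and clinical care. The primary coefficient and its 35% criterion are not involved.

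**Working it through.** **Inputs.** 40 participants (9.2); three of five scanners plus VCTE each, and the repeat pattern (4.1); formulas and bounds (9.4.2, 9.4.3). Counts assume full enrolment and balanced assignment. The documents give no numeric target for the secondary endpoints.

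**1. The plan's own exam count.** Visit 1: 2 × 2 + 1 + 1 = 6. Visit 2: 1 + 1 + 2 + 2 = 6. The total of 12 agrees with 4.1, so the repeat pattern is read correctly.

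**2. Same-day replicate pairs.**

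| | Visit 1 | Visit 2 | Both | Used as written |
|---|---|---|---|---|
| Ultrasound, all scanners | 40 × 2 = 80 | 40 × 1 = 40 | 120 | 80 |
| Ultrasound, per scanner | 80/5 = 16 | 40/5 = 8 | 24 | 16 |
| VCTE | 0 | 40 | 40 | 0 |

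**3. The divisor.** Participants per scanner: 40 × 3/5 = 24. Summing 16 available terms and dividing by 24 multiplies the coefficient by √(16/24) = 0.816. If the bound also uses N = 24, its multiplier is 1.316 instead of 1.418 (16 degrees of freedom). The bound is then 0.816 × 1.316/1.418 = 0.758 of its proper value.

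**4. Pooled different-scanner coefficient, if all pairs were counted.** For readings A, B and C at one visit, (A−B) + (B−C) = A−C. The three squared differences sum to 3 × the within-participant sum of squares, which has 2 degrees of freedom. The point estimate is unaffected, but 40 participants give 120 pairs and only 80 degrees of freedom.

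- Multiplier √(df/χ²(df, 0.05)): 1.120 at 120 and 1.151 at 80. The ratio is 0.973, so the bound is about 2.7% low.
- Coverage of the nominal 95% bound: P(χ²₈₀ ≥ 80 × χ²(120, 0.05)/120) = 90.7%. With 30 evaluable participants (25% loss), 90 against 60 degrees of freedom also gives 90.7%.
- Both visits: 240 pairs, at most 160 degrees of freedom, coverage 90.8%. If half the variance is a lasting participant-by-scanner effect (assumed), simulated coverage is about 87%.

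These figures use the lower 5% chi-square point. The printed α of 0.95, read literally, would put the bound below the estimate; that is a separate notation matter.

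**5. Fixed scanner offsets.** The documents give no size for these. With assumed equally spaced offsets over five scanners, simulated coverage using 120 degrees of freedom was:

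| Offset share of variance | Coverage |
|---|---|
| 0% | 91% |
| 14% | 91% |
| 38% | 92 to 93% |
| 58% | 95% |
| 71% | 97% |

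**6. Would a participant-level bootstrap help?** Simulated one-sided 95% percentile bootstrap with normal errors (9.4.2 names no bootstrap variant, so this is an assumption):

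| Bound | Bootstrap coverage | Chi-square, correct df |
|---|---|---|
| Pooled different-scanner, 40 participants | about 90% | about 95% |
| Per scanner, 24 participants | about 86 to 87% | about 95% |
| Per scanner pair, 40 × 3/10 = 12 participants | about 82 to 84% | about 95% |

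**The case against.** The strongest reply is that timepoint 1 is a slip. VCTE replicates are scheduled and the endpoint is declared, so an analyst would use the Visit 2 data. The arithmetic lends this some support: with both visits included, each scanner has 16 + 8 = 24 pairs, which equals the stated N_j. That is a fair guess at the intention. It does not change the written rule, which conflicts with 4.1, and the divisor is right only if the wording is corrected and no repeat is missing.

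The pooled same-day coefficient has an obvious form, the per-scanner terms summed over scanners, and raises no comparable degrees-of-freedom problem. That stands: the gap there is only an unwritten formula. The VCTE endpoints are not pooled and need no pooled formula.

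A reader might infer that the plan's different-scanner bounds are too narrow. The documents do not support this. The coefficient in 9.4.3 is for one pair of scanners, each participant gives one difference, and N degrees of freedom is right for sampling error. The bound with 120 degrees of freedom would arise only from an extension the plan never states. Even then its direction depends on scanner offsets of unknown size. No pass limit is attached to it.

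A reader might also want the bootstrap of 9.4.2 extended to every secondary bound. Step 6 argues against this: it would do no better for the pooled different-scanner bound and would worsen bounds that are now correct.

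**Conclusion.** The conflict between 9.4.3 and 4.1 is real and follows from the text alone. As written, VCTE has 0 of 40 same-day pairs, ultrasound has 80 of 120, and the literal divisor understates the per-scanner coefficient by a factor of about 0.82. This rests on timepoint 1 meaning Visit 1, as 9.4.2 uses the term, and on balanced assignment with full enrolment. It should not be read as VCTE repeats not being collected; they are scheduled at Visit 2.

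The absence of pooled estimators for two declared secondary endpoints is also real. The degrees-of-freedom consequence is conditional and moderate: about 90.7% coverage instead of 95% if all three pairs were counted as independent and there were no fixed offsets. It is a reason to write the estimator down, not an error in a stated method. The point deserves correction before analysis and does not touch the primary result.

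**What to change.** In 9.4.3:

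- Replace timepoint 1 with the same visit in the same-day formula. Take replicate pairs from whichever visit the exam was repeated at (VCTE from Visit 2), and set both the divisor and the degrees of freedom to the number of replicate pairs.
- Write the pooled same-day coefficient as the sum of these pairs over the five scanners.
- Define the pooled different-scanner, same-day coefficient from the within-participant, within-visit variance across the three scanners, with 2 degrees of freedom per participant at one named visit. State which reading of a repeated exam enters, and note that fixed scanner offsets make the chi-square bound approximate.
- Keep the chi-square bounds for the per-scanner and per-pair coefficients, and do not replace them with a percentile bootstrap.

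The cost is SAP wording and a pooled different-scanner bound slightly wider than one that counts all pairs (multiplier 1.151 against 1.120). No new data or visits are needed.

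### RDC_scanner reports only the sum of vendor offset and scatter, as worded leaves out the Visit 2 same-day pairs, and carries a chi-square bound that does not fit it

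*Combined protocol and SAP*

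**What the plan says.** The Synopsis lists as a secondary endpoint: "Evaluation of pooled different-scanner, same-day reproducibility coefficient of ultrasound-based measurements of SWS". Section 9.4.3 defines the coefficient for one pair of scanners as 2.77 times the root of the mean of (Y1−Y2)²/(2Ȳ²). Y1 is the reading at timepoint 1, and Y2 "is the biomarker measurement on a different scanner for the" same participant, with no visit stated. It adds: "This RDC will be estimated both with the same and different operators, and on the same and different days". The upper bound multiplies the estimate by √(N/χ²), where χ² is the α "th percentile of the chi square distribution with N degrees of freedom and α is 0.95".

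On the design, section 4.1 says: "For each visit, each participant will be assigned to three of the five ultrasound scanners plus VCTE", and "Each participant will undergo ultrasound imaging at Visit 1 (by operator 1) and at Visit 2 (by operator 2"). The scanners scanned twice at one visit are scanned once at the other, so all three of a participant's scanners are used on both days.

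Section 9.4.3 plans no paired mean difference between scanners, no centred coefficient, no formula for pooling over scanner pairs and no bootstrap for this coefficient. The participant-level bootstrap in 9.4.2 is stated for the primary RDC only.

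**The concern.** The scanners come from five vendors, and nothing in the documents supports a zero mean difference between them. An uncentred squared difference adds the square of that mean difference to the random variance. A large coefficient could therefore mean a constant shift, which a conversion factor could remove, or scatter, which nothing removes. Section 3 says these endpoints are meant to refine the context of use, and whether readings from several vendors can be combined depends on that split.

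Two further points concern precision. If Y1 is always a Visit 1 reading, the same-day estimate draws on one of the two days on which same-day pairs exist. And the bound uses a distribution that assumes N independent differences centred on zero, a condition that vendor offsets and shared readings both break.

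**Working it through.** **Inputs.** Section 9.2: the assumed RDC "is in the range of 20-30% (wCV of 7.2-10.8"%), and 40 participants with up to 25% loss. Section 4.1: three of five scanners per participant, two visits, one operator per visit. Section 9.4.3: the estimator and the bound. Assumptions: an offset d of 0 to 20% of the mean (no figure is given), balanced assignment, and one reading per scanner per visit.

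**Plan's own figure.** The documents state no value for RDC_scanner. The scale checks: 2.77 × 7.2% = 19.9% and 2.77 × 10.8% = 29.9%, matching 20–30%.

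**1. Offset plus scatter.** With relative differences distributed N(d, 2·wCV²), the expected square is

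RDC_total² = 2.77² × (wCV² + d²/2) = RDC_random² + 2.77²·d²/2.

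At RDC_random = 25% (square 625):

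| d | added square | total RDC | offset share of square |
|---|---|---|---|
| 5% | 95.9 | √720.9 = 26.8% | 13% |
| 10% | 383.6 | √1008.6 = 31.8% | 38% |
| 15% | 863.2 | √1488.2 = 38.6% | 58% |
| 20% | 1534.6 | √2159.6 = 46.5% | 71% |

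Over wCV 7.2–10.8% the offset share is 10–19% at d = 5%, 30–49% at 10% and 63–79% at 20%. Simulating the plan's estimator at wCV 9% gave 31.4% and 46.3% at d = 10% and 20%, against 31.7% and 46.4% from the formula.

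**2. Same-day pairs.** Three scanners give 3 pairs per participant per visit: 40 × 3 = 120 per visit and 240 over both. Five scanners form 10 pairs, so 120/10 = 12 participants per pair, or 9 after 25% loss. With Y1 fixed at Visit 1, the admissible pairs are the Visit 1 same-day pairs and the cross-visit pairs. The other 120 same-day pairs have no defined place.

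**3. Bound for one scanner pair, N = 12.**
- As printed (95th percentile, 21.03): √(12/21.03) = 0.755. The upper bound falls below the estimate.
- 5th percentile (5.226): √(12/5.226) = 1.515. At d = 0 this is exact.
- With an offset, Σ(difference²)/(2·wCV²) is noncentral chi-square with N df and λ = N·d²/(2·wCV²). If offset is half the mean square, λ = 12 and the multiplier needed is 1.43; 1.515/1.43 = 1.06, so the bound is about 6% too wide. At random RDC 25% (wCV 9.03%) this corresponds to d = √2 × 9.03% = 12.8%.
- Coverage with the 5th percentile, over wCV 7.2–10.8%: 95.1–95.3% at d = 5%, 95.7–96.9% at 10%, 98.3–99.7% at 20%.

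**4. Bound carried over to the pooled endpoint, zero offset.** A participant's three pair differences come from three readings. The sum of their squares over 2 equals 3/2 times the readings' sum of squares about their mean, which has 2 df. So 40 completers give 80 df, not N = 120. The 5th-percentile multiplier is √(120/95.70) = 1.120 with N df and √(80/60.39) = 1.151 with 80 df. The N-df bound covers about 91%. A correct bound is 1.151/1.120, about 3% wider.

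**5. Gain from Visit 2.** The relative standard error is about 1/√(2 × 80) = 7.9% from one visit and 1/√(2 × 160) = 5.6% from two, if errors are independent between visits. Any participant-by-scanner effect that persists across visits makes the gain smaller.

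**The case against.** The strongest reply is that a between-scanner reproducibility coefficient asks how far two readings may differ when the scanner changes, so scanner bias belongs in it. That stands. A reader might infer that merging offset and error is a mistake in the estimator; it is not. The gap is that the total is the only quantity reported. Section 9.4.1 plans means and SDs of the measurements, but not paired differences with an interval.

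A reader might also infer that the bound is invalid whenever an offset exists. For a single pair with the 5th percentile it is exact at zero offset and conservative otherwise, so it errs on the safe side. The excess is small for modest offsets (0.7% at N = 12 when offset is 20% of the mean square). It shrinks with N: at N = 120 and a half share it is about 1.6%, ignoring clustering. The failures of coverage are elsewhere: the printed percentile and the shared readings.

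On Visit 2, the wording may be loose drafting. The text never expressly excludes that visit. Timepoint 1 also cannot mean Visit 1 throughout 9.4.3: the same-day repeatability formula places both readings there, yet 4.1 repeats VCTE only at Visit 2. It would go too far to say that half the same-day data will certainly go unused. The sentence on same and different operators and days does not settle it, because with Y1 at Visit 1 it adds only cross-visit pairs. The second set of pairs also comes from the same participants, so information need not double.

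Finally, one might carry over the rule "If the upper 95% confidence bound is < 0.35" and speak of false passes. That rule belongs to the primary RDC; no threshold is attached to RDC_scanner.

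**Conclusion.** The point holds as a gap in reporting and specification for a secondary endpoint. It does not affect the decision rule for the primary endpoint.

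- **Offset not estimated:** certain from the text. Its size is unknown; the totals of 26.8% to 46.5% rest on assumed offsets of 5% to 20% at a random RDC of 25%.
- **Visit 2 same-day pairs:** omitted as worded (120 of 240 with 40 completers and balanced assignment), possibly unintentionally.
- **Bound:** with the 5th percentile, mildly conservative for a single pair with an offset. For the pooled endpoint it is too narrow (about 91% coverage at zero offset), taking the N-df formula as carried over, since 9.4.3 gives no other. As printed, it is not an upper bound. The percentile error is separate and needs correcting whatever is done about offsets.

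**What to change.** 1. Keep RDC_scanner as the total, and say that it includes any scanner offset.
2. For each scanner pair, report the mean of D = (Y1−Y2)/Ȳ as a percentage with a 95% CI, and the RDC after removing it: 2.77 × √[Σ(D−D̄)²/(2(N−1))].
3. Define the same-day estimate as using same-day pairs from Visit 1 and Visit 2. State which reading counts where a scanner was used twice that day, and give the formula for pooling over pairs.
4. Take bounds for the total and the offset-removed RDC from the participant-level bootstrap already specified in 9.4.2, resampling all of a participant's readings together. Correct the chi-square percentile wherever that formula stays.
5. A mixed model is optional. If one is used, allow scanner-specific residual variance, since 4.1 and 9.2 assume RDCs that differ by scanner (23–30%).

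The cost is SAP wording and modest programming, with no new data. For the pooled endpoint the bound will be somewhat wider than the N-df formula gives on the same pairs (about 3% at zero offset). With 9 to 12 participants per scanner pair, bootstrap bounds for single pairs will be rough and should be labelled as such.
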